All patients must have a baseline (pre-treatment) bone marrow aspirate (+ biopsy) and peripheral blood sample within 14 days prior to the first administration of SL-401. Subsequent bone marrow aspirate (+ biopsy) and peripheral blood assessments will be made at the end of Cycles 2, 4, and 6, then every 3 months (\pm 1 month) until Month 12. Bone marrow assessments of MRD for patients at baseline and during treatment will be conducted at a central laboratory, as described in Section 8.11.1 and the Laboratory Manual. No repeat bone marrow is necessary if progressive disease can be unequivocally diagnosed from peripheral blood tests. If the end of Cycle 2 bone marrow examination is empty (i.e., hypocellular) or inadequate, a bone marrow examination should be repeated in 14 (\pm 7) days to document response status. If additional time is required to complete the repeat examination, consult with the Medical Monitor. CD123 is to be assessed in all bone marrow samples (and, if applicable, tissue samples) by flow cytometry (i.e., CD123 should be added to the panel of markers assessed by flow cytometry of bone marrow aspirates) and immunohistochemistry and the results recorded and captured in the electronic case report form (eCRF). Peripheral blood assessment (differential) will also be performed as indicated for assessment of circulating leukemic blasts.

Patients will also be followed for RFS and OS.

Study Centers:

Patients will be recruited from up to 20 centers in the North America.

Inclusion Criteria:

1. The patient has a diagnosis of AML according to World Health Organization (WHO) criteria.
2. The patient received any induction chemotherapy regimen and may have received post-remission consolidation therapy prior to screening.
3. The patient has achieved a first or second CR or CRi. For patients without evidence of MRD in CR/CRi, CR (or CRi) must have been initially identified within 12 months prior to screening.

OR

The patient has achieved first or second CR or CRi with evidence of MRD as determined locally at

least 6 months post stem cell transplant without evidence of acute or chronic graft-versus-host disease post-transplant and has not received immunosuppressant therapy for at least 14 days prior to SL-401 therapy.

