Demographic (e.g., gender, age, and race) and baseline characteristics (e.g., ECOG performance status, height, weight, and prior therapy) will be summarized by SL-401 dose group with descriptive statistics.

Treatment-emergent AEs through 30 days after last SL-401 infusion will be summarized by the Medical Dictionary for Regulatory Activities (MedDRA™), Version 13.1 (or higher), System Organ Class and preferred term. The incidences and percentages of patients experiencing each AE preferred term will be summarized with descriptive statistics. AEs will also be summarized by National Cancer Institute Common Terminology Criteria for Adverse Events (NCI-CTCAE), Version 4.03 (or higher), grade and by causality (relationship to study drug). DLTs, Grade 3-4 AEs, SAEs, and AEs resulting in dose modification or treatment discontinuation will also be summarized by preferred term.

Laboratory results will be classified according to NCI-CTCAE, Version 4.03 (or higher). Laboratory results not corresponding to an NCI-CTCAE term will not be graded. Incidences of laboratory abnormalities will be summarized with descriptive statistics.

Vital signs and physical examination results will be summarized with descriptive statistics.

Efficacy analyses will include all patients treated at the MTD or maximum tested dose. The distributions of RFS and OS will be estimated by Kaplan-Meier methodology. The presence of MRD will be summarized at each assessment time point by descriptive statistics. Relapse-free survival will also be summarized for subgroups defined by MRD status (e.g., no MRD at baseline, MRD at baseline converting to no MRD at any time point during follow-up, MRD at baseline and at every time point during follow-up).

Sample Size:

In Stage 2, up to 20 additional patients with MRD as determined locally will enroll and receive SL-401 at either the MTD or maximum tested dose, so that a total of 15 patients with evidence of MRD as determined centrally are treated at this dose. The assumptions governing sample size are as follows:

- Null hypothesis: eradication of MRD $\leq 5\%$
- Alternate hypothesis: eradication of MRD $\geq 20\%$
- Type 1 error: 17% one-sided
- Power: $>80\%$

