6.2 Overall Study Design

This is a non-randomized, open-label, dose escalation, multicenter study, divided into 2 stages. A cycle of therapy is 28 days. A Data Safety Review Committee (DSRC), which will include Sponsor representatives, will be established to review the accruing safety data and make safety decisions during the study, including dose escalation during Stage 1. The DSRC will also periodically review data during Stage 2 (at least 2 times per year, and more frequently in the event of DLTs, other severe or serious AEs or treatment –related deaths).

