6.2.2 Stage 2: Expansion

During Stage 2, up to 20 additional patients with evidence of MRD as determined locally will be treated at the MTD or maximum tested dose at which multiple DLTs are not observed (identified in Stage 1) so that up to 15 patients with evidence of MRD as determined centrally are evaluable for safety and response at this dose. For inclusion in the study, all patients treated in the expansion phase should have MRD in bone marrow, as determined locally, via at least one of the following modalities: multi-parametric flow cytometry, cytogenetic evaluation, FISH, real-time PCR, or next-generation gene sequencing. It is anticipated that at approximately 50% of patients evaluated with AML in first remission (CR or CRi) will have evidence of MRD.

6.2.3 Tumor Assessments during Stages 1 and 2

All patients must have a baseline (pre-treatment) bone marrow aspirate (+ biopsy) and peripheral blood sample within 14 days prior to the first administration of SL-401. Subsequent assessments will be performed on the following schedules until, in the judgment of the Investigator, there is evidence of relapsed or progressive disease:

- Bone marrow aspirates (+ biopsy) and peripheral blood samples 28 (\pm 7) days after the start of Cycles 2, 4 and 6, then every 3 months (\pm 1 month) until Month 12. No repeat bone marrow is necessary if non-response or progressive disease can be unequivocally diagnosed from peripheral blood tests.
- If the Cycle 2 (Day 28 [\pm 7]) bone marrow examination is empty (i.e., hypocellular) or inadequate, a bone marrow examination should be repeated in 14 (\pm 7) days to document response. If additional time is required to complete the repeat examination, consult with the Medical Monitor.
- Bone marrow will be assessed for morphologic evidence of AML recurrence, and flow cytometric and other cytogenetic/molecular assessments, including evaluation of MRD.
- CD123 is to be assessed in all bone marrow samples (and, if applicable, tissue samples) by flow cytometry (i.e., CD123 should be added to the panel of markers assessed by flow cytometry of bone marrow aspirates) and immunohistochemistry and the results recorded and captured in the electronic case report form (eCRF). (The Cycle 2, 4, and 6, Day 28 [\pm 7 days] peripheral blood and bone marrow assessment should occur on Day 28 [\pm 7 days] even in the setting of patients receiving SL-401 over 6-10 days [as opposed to 5 consecutive days]).

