1.2.5. Efficacy, Pharmacokinetic, and Safety Parameters

1.2.5.1. Efficacy Parameters

Efficacy assessments include rates of MRD eradication (conversion), RFS, and OS. Response/remission will be assessed using International Working Group criteria for AML ([Cheson et al. 2003](#)). Response criteria for AML are summarized in [Section 8.1](#). All efficacy outcomes will be presented by subgroups defined by MRD Status and line of therapy in study (First-Line or Relapsed/Refractory). Definitions for each efficacy assessment are described in [Section 4.3](#).

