4.3.2. Relapse-Free Survival

Relapse-Free Survival is defined as the time from the date of first infusion of Tagraxofusp to the date of relapse (AML recurrence) or death from any cause, whichever occurred first. According to current WHO classification, a myeloblast population comprising greater than 5% of nucleated cells in the bone marrow or blood is required for diagnosis of AML relapse following CR/CRi

(if no peripheral blasts are present, then a confirmation aspirate is required ≥ 1 week subsequent to the aspirate at which $>5\%$ blasts were identified).

For patients who receive SCT, RFS will include time to progressive disease or death post-transplant. Patients who do not progress and are still alive at the time of analysis will be censored on the date of last treatment recorded prior to the analysis cut-off date. If patients start other anticancer therapies (with the exception of SCT or preparations for SCT), they will be censored at the latter of the date of last treatment with Tagraxofusp or date of last disease assessment recorded that occurred prior to the start of the new therapy.

The proportion of subjects receiving treatment who are alive and without evidence of AML recurrence will be presented. The distribution for RFS will be estimated by Kaplan-Meier methodology and the 25th percentile, median, 75th percentile, number and percentage of events and censored observations, and appropriate CIs will be presented. 6- and 12-month RFS rates will be evaluated.

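### Summarizing RFS from first infusion by MRD conversion at any later time favours converters in expectation, even if conversion has no effect

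*Protocol*

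**What the plan says.** The subgroups come from the Protocol Synopsis, Statistical Methods: "Relapse-free survival will also be summarized for subgroups defined by MRD status". Three groups follow as examples. One has no MRD at baseline; the other two are "MRD at baseline converting to no MRD at any time point during follow-up, MRD at baseline and at every time point during follow-up".

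Four other places decide how this works in practice:

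- **Clock.** SAP 4.3.2: "Relapse-Free Survival is defined as the time from the date of first infusion of Tagraxofusp to the date of relapse" or death.
- **Marrow schedule.** Per the Protocol Synopsis, post-baseline marrows "will be made at the end of Cycles 2, 4, and 6, then every 3 months" until Month 12. Protocol 6.2 states "A cycle of therapy is 28 days", so the first post-baseline MRD result falls at about Day 56.
- **End of assessments.** Protocol 6.2.3 continues them "until, in the judgment of the Investigator, there is evidence of relapsed or progressive disease".
- **SAP subgroups.** SAP 1.2.5.1: "All efficacy outcomes will be presented by subgroups defined by MRD Status and line of therapy in study". Sections 3.8 and 4.3 repeat this. None says whether MRD status means baseline or post-baseline status.

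Protocol 11.5.2 does not repeat the conversion subgroups. SAP 5 declares no change from the protocol's analyses, so the synopsis definition has not been withdrawn. Neither document gives a landmark, a time-dependent method, or a rule for patients who relapse before their first post-baseline marrow.

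**The concern.** The RFS clock starts before anyone can be classified. To be counted as a converter, a patient must remain relapse-free until a negative marrow is taken, and a patient who stays relapse-free longer has more marrows at which to convert. The time before conversion is event-free by definition and is credited to the converter group. This is guarantee-time (immortal-time) bias.

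The figures exposed are the median and the 6- and 12-month RFS in each group. MRD eradication is the study's activity endpoint, so a reader who sees much longer RFS in converters is likely to conclude that eradication brings clinical benefit. The display cannot support that conclusion.

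**Working it through.** **The plan's own figure.** The documents give no figure for RFS by MRD status. The nearest is the rule of at least 2 conversions in 15:

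- At 5%: 1 − 0.95^15 − 15 × 0.05 × 0.95^14 = 0.171.
- At 20%: 1 − 0.8^15 − 15 × 0.2 × 0.8^14 = 0.833.

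Both match the stated 17% and >80%. The rule counts conversions and does not use RFS time, so this bias does not reach it.

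**Inputs from the documents.** Marrows at Days 56, 112 and 168 (ends of 28-day Cycles 2, 4 and 6), then about Days 259 and 350. RFS from first infusion. Marrows stop at relapse.

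**Assumptions.**
- One-year relapse of 60%, with exponential times: S(t) = 0.4^(t/365.25). Protocol 3.1.3 cites more than 60% for MRD-positive intermediate-risk patients in remission after 2 induction cycles, which is not exactly this population.
- Each marrow is negative with probability 5%, unrelated to relapse. Conversion therefore has no effect, and true 12-month RFS is 40% for everyone.

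**Step 1: chance of being a converter.** The chance that marrow k is the first negative one is w_k = 0.05 × 0.95^(k−1), provided the patient is still relapse-free.

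| Day | S(t) | w | product |
|---|---|---|---|
| 56 | 0.869 | 0.0500 | 0.0434 |
| 112 | 0.755 | 0.0475 | 0.0359 |
| 168 | 0.656 | 0.0451 | 0.0296 |
| 259 | 0.522 | 0.0429 | 0.0224 |
| 350 | 0.416 | 0.0407 | 0.0169 |

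The products sum to 0.1482.

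**Step 2: 12-month RFS by group.**
- Converter and relapse-free at 12 months: (1 − 0.95^5) × 0.40 = 0.0905.
- Converters: 0.0905 / 0.1482 = 61%.
- Non-converters: (0.40 − 0.0905) / (1 − 0.1482) = 36%.
- Non-converters without relapses before Day 56 (1 − 0.869 = 0.131): 0.3095 / (0.8518 − 0.1311) = 43%.

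Under the same model the medians are 14.6 and 8.0 months (10.1 for non-converters with early relapses left out). Six-month RFS is 87% and 59%.

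**Step 3: other assumptions.**
- At 2% negativity per marrow, 12-month RFS is 62% and 39%; at 10% it is 60% and 33%.
- Simulations covered one-year relapse of 40–75% and total conversion of 5–40% (if every marrow is attended). The apparent hazard ratio was 0.41–0.48, or 0.52–0.63 with early relapses left out. The true ratio is 1.
- SAP 4.3.2 censors event-free patients at last treatment. Taking that as about Day 145 (Cycle 6, infusion 5), 12-month Kaplan-Meier RFS becomes 39% and 21% with an 18-month cut-off, or 50% and 28% with a 24-month cut-off.

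**Step 4: small samples.** With 60% one-year relapse and 20% total conversion, converters have the longer median in 78%, 82% and 84% of trials of 9, 15 and 20 patients in which both groups exist. With early relapses left out these are 70%, 73% and 74%. An unbiased display would give about 50%.

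**Step 5: with the bias removed.**
- From a Day 56 landmark, the chance of being relapse-free at 12 months is 0.40 / 0.869 = 46% in both groups.
- Across the Step 3 simulation ranges, landmark (end of Cycle 2) and time-dependent hazard ratios lie between 0.99 and 1.02.
- The landmark's converter group would be small. The chance of converting at Day 56 is 0.05 × 0.869 = 0.0434 per patient. With 9 patients, 0.4 converters are expected and none occur in 0.9566^9 = 67% of trials. With 15 patients, 0.7 are expected and none occur in 51%.

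**The case against.** The strongest case is that the plan asks for little here. RFS is to be summarized, the groups are examples, and they appear only in the synopsis. SAP 3.2 confines formal testing to the MRD eradication rate, and SAP 3.6 calls the subgroup analyses exploratory and descriptive. A reader might infer that the plan formally compares RFS between converters and non-converters. It does not: no test or hazard ratio is planned, and no stated objective asks whether conversion predicts RFS.

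The SAP pairs MRD status with line of therapy, a baseline factor. Baseline status is a plausible reading, and it would carry no guarantee-time bias. That weakens the point but does not remove it, because the SAP neither says so nor withdraws the synopsis definition.

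A reader might also infer that patients who relapse before Day 56 must be counted as MRD-persistent. The documents do not say where a patient without a post-baseline marrow belongs, so both figures are shown above. In one special case the bias disappears: if conversion occurs only at the end-of-Cycle-2 marrow and earlier relapses are left out of both groups, both medians are 10.9 months. The any-time wording does not limit conversion in that way.

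The objection that a landmark would often have no converters stands, and it shapes the fix.

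**Conclusion.** The concern holds for a descriptive secondary summary. If the synopsis definition is followed with RFS timed from first infusion, the display favours converters in expectation with no true effect: about 61% against 36% at 12 months, or 61% against 43% with early relapses left out.

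The size depends on assumptions the documents do not supply: exponential relapse, 60% at one year, and a constant 5% chance of a negative marrow. The model also omits the End-of-Treatment marrow. The SAP's censoring rule shifts the levels, so 61% and 36% are not what the SAP's tables would print. The direction was the same in every any-time scenario tried, with early relapses kept or left out.

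Two stronger readings are not supported. Converters are not certain to look better in this trial; at 9 to 20 patients that happens in roughly 70–84% of trials with both groups present. Nor does the bias touch the MTD and safety objectives or the rule of at least 2 conversions in 15.

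The SAP should be corrected on this point, but the study's main conclusions do not depend on it.

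**What to change.** In the SAP (3.8, 4.3 and 4.3.2):

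1. Define MRD status for RFS timed from first infusion as baseline MRD status only.
2. Show any RFS-by-conversion result in one of two ways, labelled exploratory:
   - with conversion as a time-dependent status (Simon-Makuch plot); or
   - from a fixed landmark at the end-of-Cycle-2 marrow (Day 56 ± 7), with the RFS clock starting there and the numbers who relapsed, died or left before it reported.
3. If the converter group is empty or has only one or two patients, show the by-patient listing of conversion and relapse dates instead. SAP 4.3 already plans by-patient listings of all efficacy endpoints.

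The cost is SAP wording and minor programming, with no new data. The downside is that later converters and early relapsers (about 13% by Day 56 under the assumptions above) do not count as converters in the landmark display. With 9 to 15 MRD-positive patients (SAP 3.1 reports 9 enrolled in Stage 2), the listing may be all that can usefully be shown.

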3.1 Acute Myeloid Leukemia

Acute Myeloid Leukemia (AML) is characterized by the uncontrolled proliferation of immature myeloid cells in the bone marrow and peripheral blood, resulting in the development of anemia, neutropenia, and thrombocytopenia, and associated complications such as serious infections, bleeding, and fatigue. The American Cancer Society (2013) estimates there will be approximately 14,590 new cases of AML in the United States (US) during 2013, with an estimated 10,370 deaths due to the disease. The median age at diagnosis is 67 years, and 5-year survival across all ages, treatments, and other prognostic subgroups is 24% ([National Cancer Institute 2013](#)). The World Health Organization (WHO) classification of AML incorporates morphology, cytogenetics, molecular genetics, and immunologic markers to define clinically relevant disease entities that are universally applicable and prognostically valid with therapeutic implications ([Bennett et al. 1976](#); [Bunning et al. 2001](#); [Cheson et al. 1990](#); [Cheson et al. 2007](#)).

3.1.1 First-line Therapy Including Induction and Consolidation

Initial treatment of AML is divided into induction chemotherapy and post-remission, consolidation therapy. To optimize potential for durable remission, patients frequently receive some form of consolidation therapy, which is routinely given to patients aged <60 years and generally involves multiple courses of intensive chemotherapy or stem cell transplantation (SCT) ([Dohner et al. 2010](#)). Consolidation therapy is often given only once, or not given at all, to patients who are > 60 years of age. Tolerance of the induction and consolidation phases is directly related to patient characteristics such as age, the presence or absence of comorbidities, and performance status. Strategies for consolidation are generally based on the risk of relapse, with more adverse risk patients receiving more aggressive therapy. Current first-line induction treatments for AML among eligible patients include chemotherapy drugs such as cytarabine, daunorubicin, and mitoxantrone. Post-remission consolidation therapies include dose-intensified cytarabine, and autologous or allogeneic SCT.

Although complete remission (CR) rates after standard first-line induction therapy in AML are relatively high, certain subgroups of patients with AML often cannot tolerate treatment strategies which optimize the probability of durable remissions, or have a high risk of relapse even when available standard therapies are administered. Consequently, National Comprehensive Cancer Network Guidelines (2013) recommend that AML patients with an antecedent hematologic disease (e.g., myelodysplasia, myelofibrosis, polycythemia vera), age > 60 years, or unfavorable cytogenetics (e.g., deletion of 5 or 7 and ≥ 3 abnormalities) are appropriate candidates for clinical studies with novel agents early in their disease (i.e., as first-line therapy or during an initial remission).

3.1.2 Adverse-Risk AML

In recent decades, there has been substantial progress in the characterization of the genetic and molecular basis of AML and in the identification of both clinical and laboratory-based

prognostic factors. The 2008 WHO classification included many of these factors into the categorization of AML into favorable, intermediate, and adverse risk groups ([Swerdlow et al. 2008](#)). The very substantial risk of relapse and mortality for patients with adverse, and even intermediate risk AML, has increasingly been appreciated in recent years, including patients who are able to receive SCT and especially for patients who are not candidates for SCT. Cytogenetic abnormalities that are associated with adverse risk status include chromosomal deletions (-5, -5q, -7, -7q), additions (add[5q], add[7q]), translocations (t[11q23], t[6;9] and many others), inversions (inv[3][q21q26]) and complex abnormalities (≥ 3 unrelated abnormalities) ([Morrisette and Bagg 2011; Hasserjian 2013](#)). In a consolidated analysis of younger adults treated on multiple AML studies sponsored by the United Kingdom's Medical Research Council (MRC), 5-year overall survival for patients with inv(3)/t(3;3) or complex karyotype was less than 10%. It is worth noting that in this analysis, 5-year overall survival for patients with selected intermediate risk AML was less than 35% ([Grimwade 2001](#)). Additional AML-related mutations associated with adverse risk include FLT-3 internal tandem duplications (FLT3-ITD). In the aforementioned MRC pooled analysis, 5-year overall survival (OS) for patients with FLT3-ITD mutations was less than 15%. Even in the absence of karyotypic abnormalities, FLT3-ITD mutations are associated with adverse prognosis; in an analysis of patients without cytogenetic abnormalities enrolled on several studies sponsored by the German-Austrian AML Study Group, 5-year overall survival (OS) was less than 30% for patients with FLT3-ITD mutations (and was lower for the subset for whom HLA-matched SCT donors were not available) ([Schlenk et al. 2008](#)).

3.1.3 Minimal Residual Disease (MRD) in AML

For AML patients who achieve hematologic remission following induction therapy, the evaluation of MRD confers additional information concerning the risk of relapse and mortality, and increasingly is considered a factor as additional therapeutic options are considered. Multi-parametric flow cytometry for detection of leukemia-associated phenotypes (LAIPs) has become a valuable mechanism for investigation of potential MRD in the bone marrow aspirates of AML patients in remission. LAIPs include asynchronous expression of antigens (i.e., aberrant expression of antigens across maturation stages, such as coexpression of early and late antigens), cross-lineage expression of lymphoid markers, and overexpression or absence of lineage-appropriate markers. Additional methods by which MRD may be evaluated include cytogenetic or fluorescence *in situ* hybridization (FISH) assessment for chromosomal translocations (including those defining adverse risk AML), real-time polymerase chain reaction (PCR)-based assessment of gene mutations, and next generation sequencing for the persistence of somatic mutations in the coding sequence of AML-associated mutations (for example: the MD Anderson Cancer Center 28-gene AML panel, which includes gene mutations associated with adverse risk AML and others including IDH1, IDH2, DNMT3A, ASXL1, TET2, N-RAS, and K-RAS) ([Ravandi and Jorgensen 2012; Jorgensen et al. 2011](#)).

The identification of MRD upon achievement of AML remission has been associated with higher rates of relapse and diminished survival in several prospectively treated AML cohorts. In several hundred older AML patients participating in the United Kingdom National Cancer Research Institute AML16 study, patients in CR after a single course of induction therapy had 4-year OS rates of 40% and 18% respectively, depending on the absence or presence of MRD. (A similar difference was identified for patients who were in complete remission after 2 courses of induction therapy.) Survival differences based on MRD status were apparent in patients with both intermediate and adverse risk AML (the paucity of patients with favorable risk AML in this older cohort renders comparison within this group difficult) ([Freeman et al. 2013](#)). In the Dutch-Belgian/Swiss Hemato-Oncology Cooperative Group and the Swiss Group for Clinical Cancer Research AML 42A study involving more than 500 younger AML patients (aged 18-60 years), the presence of MRD upon remission was associated with higher relapse rates, which were evident at both early and intermediate (3-4 year) evaluation; the differences were apparent whether MRD was assessed after 1 or 2 induction cycles or after consolidation therapy, and in favorable, intermediate and adverse risk AML patients. As an example, for patients with intermediate risk AML in remission after 2 cycles of induction therapy, 1-year relapse rates were >60% for those with evidence of MRD versus <30% for those without MRD ([Terwijn et al. 2013](#)).

